5.8 Missing or Incomplete Date for Prior or Concomitant Medications

Missing or incomplete medication start or stop dates will be imputed for the purpose of determining whether the medication is taken concomitantly or not (see [Section 12](#) for definition). When the chronological order of medication use relative to the study drug treatment period is unclear due to missing or incomplete date(s), the medication will be considered as concomitant. The imputation algorithms will be detailed in the analysis dataset specification document. The missing or incomplete dates as captured on the eCRF will be displayed in the data listings.

5.9 Missing or Incomplete Date for Adverse Events

Missing or incomplete adverse event (AE) start dates will be imputed for the purpose of determining whether the AEs are treatment-emergent or not (see [Section 15.2](#) for definition). When the chronological order of an AE onset relative to the study drug treatment period is unclear due to missing or incomplete date(s), the AE will be considered as treatment-emergent. The imputation algorithms will be detailed in the analysis dataset specification document. The missing or incomplete dates captured on the eCRF will be displayed in the data listings.

5.10 Missing Severity Assessment for Adverse Events

If the severity is missing for an AE starting on or after the date of the first dose of study drug, then a severity of “Severe” will be assigned. The imputed values for severity assessment will be used for incidence summaries, while the actual values will be used in data listings.

5.11 Missing Relationship to Study Drug for Adverse Events

If the relationship to study drug is missing for an AE starting on or after the date of the first dose of study drug, a causality of “Related” will be assigned. The imputed values for relationship to study drug will be used for incidence summaries, while the actual values will be presented in data listings.

5.12 Character Values of Clinical Laboratory Variables

If the reported value of a clinical laboratory variable cannot be used in a statistical analysis due to, for example, a character string reported for a numeric variable, an appropriately determined coded value may be used in the statistical analysis. The coding algorithms will be detailed in the analysis dataset specification document. The actual values as reported in the database will be presented in data listings.

6. STUDY ENROLLMENT

The number of subjects screened, subjects screen failed, and subjects dosed will be summarized. Data listings of subject enrollment and subject eligibility (i.e. inclusion/exclusion criteria) will be provided.

7. SUBJECT DISPOSITION

The number and percentage of subjects who completed the study or discontinued early and the reason for study discontinuation will be summarized using the Safety Analysis Set.

The number of caregivers who consented and participated in the optional exit interview, and the number of subjects who took commercially marketed trofinetide within 30 days after study completion will also be summarized using the Safety Analysis Set.

8. PROTOCOL DEVIATIONS

Protocol deviations will be reviewed periodically over the course of the study. The review process, definition of the deviation categories, and the classification of a deviation as major or minor are detailed in the Protocol Deviation Management Plan. Protocol deviations will also be assessed with respect to relationship to the COVID-19 PHE. A summary of the number and percentage of subjects with major protocol deviations for each deviation category will be presented for the Safety Analysis Set. Three data listings of all protocol deviations, COVID-19-PHE related protocol deviations, and non-COVID-19-PHE related protocol deviations will be provided.

9. DEMOGRAPHICS AND BASELINE CHARACTERISTICS

Demographics and baseline characteristics will be summarized for the Safety Analysis Set using descriptive statistics. Variables include, but are not limited to, age at screening, sex, race, race subgroup (white vs non-white), ethnicity, height, weight, BMI, RTT-CSS total score at Screening, Baseline Overall Quality of Life score, and Baseline CGI-S score.

10. MEDICAL HISTORY

Medical history reported terms will be coded with Medical Dictionary for Regulatory Activities (MedDRA) version 24.0. The subject incidence will be summarized for each system organ class (SOC) and preferred term (PT) for the Safety Analysis Set. A subject will be counted only once per SOC or per PT for the summary.

A listing of the SOC, PT, body system, verbatim for the medical history condition/event, start and stop dates (when available), and an indicator for whether or not the condition is ongoing will be provided.

Rett Syndrome History

The age at Rett syndrome diagnosis, the age at symptoms first noticed, the number and percentage of subjects by *MECP2* gene mutation, and the number and percentage of subjects with more than one *MECP2* mutation (Yes, No) collected on the Rett History eCRF page will be summarized.

Rett syndrome history will be listed.

10.1 *MECP2* MUTATION GROUPINGS

The number and percentage of subjects will be examined in the following *MECP2* mutation groupings.

Mutations	Code in EDC	Category	Severity
R106W	1	R106W	Severe
R133C	2	R133C	Mild
T158M	3	T158M	Moderate
R168X	4	R168X	Severe
R255X	5	R255X	Severe
R270X	6	R270X	Severe
R294X	7	R294X	Mild
R306C	8	R306C	Mild
C298G (L100V)	9	Other mutations	Mild
G317A (R106Q)	10	Other mutations	Mild
C421G (Y141X)	11	Other mutations	Unknown
C455G (P152R)	12	Other mutations	Severe
C302G (P101R)	13	Other mutations	Severe
C401G (S134C)	14	Other mutations	Severe
C423G (Y141X)	15	Other mutations	Unknown
C468G (D156E)	16	Other mutations	Mild
C674G (P225R)	17	Other mutations	Mild
C965T (P322L)	18	Other mutations	Mild
710del1	19	Other mutations	Severe
806del1	20	Other mutations	Severe
807del1	21	Other mutations	Severe
1157del41	22	C-terminal Truncations	Mild
1157del44	23	C-terminal Truncations	Mild

Mutations	Code in EDC	Category	Severity
1163del26	24	C-terminal Truncations	Mild
1163del35	25	C-terminal Truncations	Mild
1164del44	26	C-terminal Truncations	Mild
1168del6	27	C-terminal Truncations	Mild
Exon 1+2	28	Large Deletions	Severe
Exon 3	29	Large Deletions	Severe
Exon 3+4	30	Large Deletions	Severe
Exon 4	31	Large Deletions	Severe
Exons 1-4	32	Large Deletions	Severe
All Others	33	Other mutations	Derived from CRF

Missing and unknown severity will not be imputed.

11. EXTENT OF EXPOSURE AND TREATMENT COMPLIANCE

Extent of exposure and treatment compliance will be summarized as both continuous variables and categorical variables for the Safety Analysis Set.

11.1 Exposure to Study drug

Duration of exposure to study drug will be calculated for each subject as (last dose date – first dose date + 1). The number and percentage of subjects within each of the following exposure levels in terms of duration of exposure will also be tabulated: <2 weeks (1 to 13 days), 2 to <4 weeks (14 to 27 days), 4 to <8 weeks (28 to 55 days), 8 to <12 weeks (56 to 83 days), 12 to <24 weeks (84 to 167 days), 24 to <52 weeks (168 to 363 days), 52 to <78 weeks (364 to 545 days), 78 to <104 weeks (546 to 727 days), and >=104 weeks (728 days or longer).

11.2 Measurement of Treatment Compliance

The study drug is provided in liquid form supplied in a 500 mL bottle. Study drug compliance will be calculated based on the drug accountability and dose modification data as collected on the eCRF. The study drug compliance will be calculated as (the total volume of drug actually taken (in mL) divided by the total volume of drug expected to be taken)*100.

The total volume of drug expected to be taken will be based on the duration of exposure and dosing schedule (see [Table 1](#)). However, if there is any dose modification prescribed by the investigator due to intolerance, the total drug expected to be taken will be adjusted accordingly to account for the modified prescribed dose schedule as recorded in the EDC.

The total volume of drug actually taken will be calculated as (total drug dispensed – total drug returned) (height in cm of drug remaining converted into volume in mL based on the following conversion [Table 3](#)).

Treatment compliance will be summarized as a categorical variable. The number and percentage of subjects within each of the following compliance levels will be tabulated: <80%, 80 to 120% and >120%.

Details of treatment compliance calculation are provided in a separate programming specifications document.

Table 3 Conversion of Height of Remaining Liquid (cm) into Volume (mL)

Height of Remaining Liquid (cm)	Estimated Volume (ml)	Height of Remaining Liquid (cm)	Estimated Volume (ml)
0.5	18	7.0	248
1.0	35	7.5	266
1.5	53	8.0	283
2.0	71	8.5	301
2.5	89	9.0	319
3.0	106	9.5	336
3.5	124	10.0	354
4.0	142	10.5	372
4.5	159	11.0	389
5.0	177	11.5	407
5.5	195	12.0	425
6.0	212	12.5	443
6.5	230	13.0	460

12. PRIOR, CONCOMITANT, AND POST-TREATMENT MEDICATION

Prior medication is defined as any medication with stop dates prior to the date of the first dose of study drug. Concomitant medication is defined as any medications that are ongoing at the first dose of study drug or with a start date between the dates of the first and last doses of study drug, inclusive. Post-treatment medication is defined as any medication with a start date after the date of the last dose of study drug. Medications will be coded using WHO Drug Global Dictionary March 2021.

The number and percentage of subjects taking concomitant and post-treatment medications will be tabulated separately by each drug class (ATC Level 3) and medication PT for the Safety Analysis Set. Multiple medication usage by a subject in the same category will be counted only once. Listing of prior, concomitant and post-treatment medications will also be provided.

COVID-19 Infection Related Medications

Concomitant medications related to COVID-19 Infection will also be listed.

13. EFFICACY ANALYSES

Unless otherwise specified, all efficacy analyses will be performed using the Safety Analysis Set. No hypothesis testing is planned. Descriptive summaries of all efficacy endpoints will be presented.

13.1 Exploratory Efficacy Endpoints

The exploratory efficacy endpoints are:

- CGI-I score at Weeks 2, 4, 8, 12, 24, 52, 78, and 104
- Change from Baseline to Weeks 2, 4, 8, 12, 24, 52, 78, and 104 in CGI-S score
- CaGI-I score at Weeks 12, 24, 52, 78, and 104
- Change from Baseline to Weeks 12, 24, 52, 78, and 104 in Overall Quality of Life Rating of the ICND Scale

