 - In addition to the two PK samples taken at Baseline, two PK samples will be taken at each subsequent visit (or upon early termination [ET]) in Treatment Period A, for a total of ten postdose PK samples over the duration of the study. At Visit 3, Visit 4, Visit 5, and Visit 6, the two PK samples will be collected at one of the following time intervals: 1-3 hours after dosing, 4-7 hours after dosing, 8-11 hours after dosing. Every subject should provide at least two PK samples from each of the specified time intervals over the course of Visits 3 through 6 (1-3 hours after dosing, 4-7 hours after dosing, and 8-11 hours after dosing). The two PK samples taken within a time interval should be collected at least one hour apart.
 - When possible, an additional PK sample will be collected from subjects who experience any SAE or experience an AE leading to discontinuation as soon as possible after the occurrence of that event.
- Study drug will be dispensed at the site during the Baseline visit when the visit is conducted in the clinic. For the remainder of the study, investigational product will be shipped directly to the subject. Study drug shipment, return, and accountability will be performed in accordance with the drug distribution plan.

Final Version: 1.0

Table S-2 Schedule of Events and Assessments for Study ACP-2566-009 (Treatment Period B, and Safety Follow-Up)

Period	Treatment Period B			Safety Follow-Up ^g	
Visit	Week 24	Week 52 (12 months)	Week 78 (18 months)	Week 104 EOT/ET (24 months)	EOT/ET +30 days
Visit Number	7	8	9	10	
Visit window (days)	±7	±7	±7	±7	+4
Type of Visit ^a		Clinic o	or Off-site		Telephone or Telemedicine
Physical examination ^a	X	X	X	X	
Vital signs ^b	X	X	X	X	
Height				X	
Weight ^a	X	X	X	X	
Electrocardiogram (ECG) ^a	X	X	X	X	
Clinical laboratory tests	X	X	X	X	
Urinalysis	X	X	X	X	
Blood samples for pharmacokinetics ^c				X ^c	
Clinical Global Impression— Improvement (CGI-I)	X	X	X	X	
Clinical Global Impression–Severity (CGI-S)	X	X	X	X	
Caregiver Global Impression– Improvement (CaGI-I)	X	X	X	X	
Overall Quality of Life Rating of the Impact of Childhood Neurologic Disability (ICND) Scale	X	X	X	Х	
Dispensing and review of semi- structured caregiver diary	X	X	X	X ^d	
Concomitant medications	X	X	X	X	X
Assessment of adverse events	X	X	X	X	X
Optional caregiver interview ^e	X				
Authorization of study drug dispensation ^f	XX				
Study drug return ^f	X			X	
Study drug accountability ^f	X	X	X	X	

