1.4.1 Rationale for Study Design

A placebo-controlled study design is not feasible in this population because of the small numbers of patients with Rett syndrome in this restricted age range. It would be necessary to randomize a large number of patients in order to make any conclusions about differences between patients treated with active drug and those treated with placebo. In addition, interpretation of the efficacy data for an interventional treatment during the regression phase of RTT would present a challenge. The pattern and timing of the regression period varies among patients and would be difficult to characterize even in a large controlled study. The design of the Phase 3 Study 003 was deliberate in attempting to reduce the impact of disease variability in the evaluation of efficacy of trofinetide in RTT: an age cut-off of ≥5 years was selected for both the Phase 2 Study 002 and the Phase 3 Study 003 and both studies have an inclusion criterion requiring the patients to be post-regression at Screening.

Because demonstrating efficacy is not the primary focus of this study, the starting dose is relatively low and increases toward the target dose are made each week in a stepwise fashion, taking into account how well the subject tolerates the medication (see Section 1.4.2). PK data

Final Version: 1.0

Final Version: 1.0 Clinical Study Protocol Amendment 2 Date: 19 December 2022

collected during treatment will provide information on the exposure to drug achieved by the doses the subjects reach, and can later be compared to the exposures associated with benefit in the other studies of trofinetide in RTT. Data from 10 patients is sufficient to provide the PK and tolerability data that may be compared to the data from studies of older patients with RTT.

Period A is 12 weeks long to mirror the 12-week length of Study 003. Period B mirrors the open-label studies, Study 004 and Study 005.

Like Study 005, Period B is designed to give subjects in the study the ability to receive open-label treatment with trofinetide until it becomes commercially available in the US, or until development of trofinetide for RTT is discontinued.

It is estimated that the length of the study will provide enough time on treatment from the time the first subject enters the study until trofinetide is available, or until it becomes apparent that trofinetide will not be marketed in the US.

1.4.2 **Rationale for Dose Selection**

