2.2.1 Exploratory Efficacy Endpoints

The exploratory efficacy endpoints for this study are:

- Clinical Global Impression–Improvement (CGI-I) score at Weeks 2, 4, 8, 12, 24, 52, 78, and end of treatment (EOT)
- Change from Baseline to Weeks 2, 4, 8, 12, 24, 52, 78, and EOT in Clinical Global Impression–Severity (CGI-S) score
- Caregiver Global Impression–Improvement (CaGI-I) score at Weeks 12, 24, 52, 78, and EOT
- Change from Baseline to Weeks 12, 24, 52, 78, and EOT in Overall Quality of Life Rating of the Impact of Childhood Neurologic Disability (ICND) Scale

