4.3 Subject Withdrawal of Consent

In accordance with the Declaration of Helsinki and other applicable regulations, legally acceptable representatives (LARs) consenting on behalf of subjects have the right to withdraw the subject from the study at any time, and for any reason, without prejudice to her future medical care.

If the LAR decides to withdraw consent on behalf of the subject from all components in the study, this must be documented and no additional assessments will be performed. The Sponsor may retain and continue to use any data collected before such a withdrawal of consent. The LAR may request destruction of any samples taken and not tested, prior to their withdrawal of consent, and the investigator must document this in the site study records.

If the LAR wants to discontinue treatment on behalf of the subject and agrees to the evaluations specified at the EOT/ET visit and/or at safety follow up (whichever is applicable), as outlined in Table S–2, the agreed assessments should be conducted. The subject's reason for wanting to discontinue treatment and the agreement to continue with the applicable assessments for study termination must be documented.

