4.4.2 Handling of Subject Discontinuation During the Treatment Period

Unless the LAR has withdrawn consent on behalf of the subject to be contacted for this study, every reasonable effort should be made to complete Visit 10 or the early termination (ET) visit and the safety follow-up (as outlined in Table S–2) if a subject discontinues during the treatment period of the study for any reason. All information will be reported on the applicable pages of the electronic case report form (eCRF).

If a subject is discontinued from the study because of an AE, every reasonable attempt should be made to follow and appropriately treat the subject until the AE resolves or until the Investigator deems the AE to be chronic or stable. For subjects who continue to be followed for safety, SAEs should continue to be reported as described in Section 7.4.2. All SAEs will continue to be followed and appropriately treated until such events have resolved or the Investigator deems them to be chronic or stable.

Pharmacokinetic samples will also be collected, if possible, at any ET visit or the visit immediately following any SAE or following any AE leading to discontinuation, even if it is an unscheduled visit.

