9.5.4 Efficacy Analyses

Descriptive summary statistics for the CGI-I and CaGI-I (observed value only), and for the CGI-S and ICND QoL score (observed values and change from Baseline) will be summarized by visit using the Safety Analysis Set.

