5.6 Analysis Visit Windows

Efficacy, safety, and PK assessments will be summarized by analysis visit as presented in Table 2 below.

Table 2 Analysis Visit Windows

Analysis Visit	Study Visit	Target Study Day	Study Day Interval
Baseline (Day 1)	2	1	≤ 1
Week 2	3	15	2 – 21
Week 4	4	29	22 – 42
Week 8	5	57	43 – 70
Week 12	6	85	71 – 126
Week 24	7	169	127 – 266
Week 52	8	365	267 – 455
Week 78	9	547	456 – 637
Week 104	10	729	638 – 759

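### Does ending the exploratory efficacy endpoints at Week 104 in the SAP, where the protocol says EOT, drop an end-of-treatment summary?

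*SAP*

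**What the plan says.** Protocol 2.2.1 gives the CGI-I "score at Weeks 2, 4, 8, 12, 24, 52, 78, and end of treatment (EOT"; the CGI-S change, CaGI-I and ICND change also finish at EOT. SAP 13.1 gives "CGI-I score at Weeks 2, 4, 8, 12, 24, 52, 78, and 104" and finishes the other three at Week 104 too.

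On presentation, protocol 9.5.4 states that the four measures "will be summarized by visit using the Safety Analysis Set". SAP 14.1 follows this and points to SAP 5.6, where "Efficacy, safety, and PK assessments will be summarized by analysis visit as presented in Table 2 below". Table 2 has Baseline and eight week rows, the last being Week 104 (Days 638 to 759).

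SAP 5.6.1 places ET assessments in these windows by study day. SAP 5.6.2 then takes the assessment nearest the target day, with ties going to the later one. Both sections send all assessments to the listings.

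The column for Visit 10 in protocol Table S-2 is headed "Week 104 EOT/ET (24 months".

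**The concern.** The two endpoint lists differ in their last entry for all four endpoints, yet SAP 20 declares no change to the protocol's analyses. A reader who takes EOT to mean the last rating on leaving treatment, whenever that happens, would expect a row that collects those ratings. None is planned.

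Early exit is foreseen. Protocol 1.4.1 says Period B gives girls the "ability to receive open-label treatment with trofinetide until it becomes commercially available in the US" or until development stops. Protocol 4.4.2 says that "every reasonable effort should be made to complete Visit 10 or the early termination (ET) visit", so the ratings should exist.

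Under the windowing rule an ET rating can be shown under a later nominal week, or can lose to a nearer scheduled rating and appear only in listings. CaGI-I and ICND ratings at an ET on Days 2 to 70 fall in the Week 2, 4 or 8 windows, where SAP 13.1 lists no such endpoint. At stake is whether the tables let a reader see, as a group, how the girls were rated when treatment ended.

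**Working it through.** **Step 1: what EOT denotes.** The protocol's endpoint list set against its assessment schedule:

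| Measure | Timepoints in protocol 2.2.1 | Post-Baseline visits in protocol 6.2 |
|---|---|---|
| CGI-I, CGI-S | Weeks 2, 4, 8, 12, 24, 52, 78, EOT (8) | Visits 3 to 10 (8) |
| CaGI-I, ICND | Weeks 12, 24, 52, 78, EOT (5) | Visits 6 to 10 (5) |

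The match is one to one, with EOT in the place of Visit 10. Protocol 6.3.4 calls Visit 10 Week 104. Protocol 6.5 identifies the final study visit as Week 104 and EOT/ET together. SAP 15.4 uses a single combined label for Week 104, EOT and ET. SAP 13.1 therefore names the same visit by its week.

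**Step 2: whether the wording removes a table.** Protocol 9.5.4 specifies summaries by visit and nothing else for efficacy. Had SAP 13.1 said EOT, SAP 14.1 would still tabulate by the Table 2 windows. The absence of a separate EOT/ET row comes from the by-visit design, which both documents share.

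**Step 3: where an early-exit rating goes.** Inputs are the windows and targets in SAP Table 2 and the nearest-to-target rule. Assumptions: exit on Days 2 to 728, earlier visits held on their target days, ET rating made on the exit day. In each window:

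- before target = target − first day (ET rating tabulated under that week)
- after target = last day − target (the scheduled rating is nearer, so the ET rating is listed only)

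| Window | Days | Target | Before | On | After |
|---|---|---|---|---|---|
| Week 2 | 2–21 | 15 | 13 | 1 | 6 |
| Week 4 | 22–42 | 29 | 7 | 1 | 13 |
| Week 8 | 43–70 | 57 | 14 | 1 | 13 |
| Week 12 | 71–126 | 85 | 14 | 1 | 41 |
| Week 24 | 127–266 | 169 | 42 | 1 | 97 |
| Week 52 | 267–455 | 365 | 98 | 1 | 90 |
| Week 78 | 456–637 | 547 | 91 | 1 | 90 |
| Week 104 | 638–728 | 729 | 91 | – | – |
| Total | 727 | | 370 | 7 | 350 |

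CGI-I and CGI-S: 370 + 7 + 350 = 727.

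CaGI-I and ICND: 69 (Days 2 to 70, no listed endpoint) + 336 (14 + 42 + 98 + 91 + 91) + 4 + 318 (41 + 97 + 90 + 90) = 727.

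**Step 4: what the counts are worth.** They are calendar days; no document gives exit timing, so they cannot be turned into numbers of girls. Two further points reduce them:

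- Of the 370 days before target, 3 + 3 + 3 (Weeks 2, 4, 8) + 7 × 4 (Weeks 24, 52, 78, 104) = 37 lie inside the protocol's own visit window for that week, so the rating is on schedule. For CaGI-I and ICND it is 7 × 4 = 28 of 336.
- Days 722 to 728 are inside the Week 104 visit window (729 − 7 = 722) and are not early exits. Stopping at Day 721 leaves 720 days, of which 350 are listing-only.

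On the listing-only days the girl still contributes her scheduled rating to that row, so she is not lost from it.

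**The case for a change.** The best case for a change is that the one-visit reading settles matters only for girls who reach Week 104. Table S-2 puts ET in the same column as Week 104, and protocol 4.3 speaks of a girl whose representative "agrees to the evaluations specified at the EOT/ET visit", as though EOT and ET were one assessment. On that reading EOT in 2.2.1 could include ET ratings, and the SAP's Week 104 row does not gather them: an ET on Day 440 loses to a Week 52 visit on Day 365, and an ET on Day 267 is shown as Week 52, 98 days ahead. SAP 15.3 already plans a last post-Baseline summary for laboratory values, so one for efficacy would be cheap.

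Part of this stands. Protocol 2.2.1 does not say whether EOT includes ET, and the SAP tables will not show final ratings as a group. But protocol 4.4.2 names Visit 10 and the ET visit as alternatives, and no section asks for a pooled EOT/ET timepoint.

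The pooled row would also be hard to read. It could combine ratings from about Day 2 to about Day 736 (729 + 7), some made after the last dose, in 10 to 15 girls. Protocol 1.4.1 itself warns that the timing and pattern of regression make efficacy difficult to interpret at this age. With so few girls, the listings show each final rating beside its study day, which tells the reader more than a pooled mean.

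**Conclusion.** No change to the plan follows. The two documents give the last timepoint different names, and for a girl who reaches Visit 10 the names mean the same visit. No analysis specified in the protocol has been removed, so the statement in SAP 20 is not contradicted. For early exits the SAP has a pre-specified rule, the by-visit rows it yields are sound, and every rating is listed. Early CaGI-I and ICND ratings on Days 2 to 70 are a small gap that analysts can fill by listing them.

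Aligning the two labels would be tidy but would alter no result. A last-rating row is an optional extra for exploratory, descriptive endpoints with no hypothesis test.

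This rests on reading EOT in protocol 2.2.1 as Visit 10, which the visit-by-visit match supports but the text does not state outright. The table specifications are in separate documents, so what can be said is that the SAP plans no EOT/ET row, not that no table will have one.
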